Continuous Glucose Monitoring in Patients with End-Stage Kidney Disease and Burnt-Out Diabetes

1. Study Summary

| | |
|---|---|
| Project Title | Continuous Glucose Monitoring in Patients with End-Stage Kidney Disease and Burnt-Out Diabetes |
| Project Design | Observational cross-sectional study. |
| Primary Objective | 
To determine if utilizing Continuous Glucose Monitor (CGM) devices is superior to HbA1c for assessing glycemic control in patients with end-stage kidney disease on dialysis. |
| Secondary Objective(s) | 
Compare daily mean glucose values between patients with burnt-out diabetes and non-diabetic subjects with ESKD. |
| Research Intervention(s)/Interactions | 
Continuous glucose monitoring (CGM) compared to glycemic metrics including CGM and HbA1c. |
| Study Population | Individual with and without diabetes on hemodialysis and with HbA1c < 6.5% on no diabetes therapy will be eligible to enroll. |
| Sample Size | 40 patients. 20 patients with burnt-out diabetes and 20 non-diabetic subjects with ESKD |
| Study Duration for individual participants | 10 days |
| Study Specific Abbreviations/ Definitions | POC, Bedside point-of-care; CGM, Continuous glucose monitoring; T2D, Type 2 diabetes; BG, blood glucose; OAD, Oral antidiabetic; MARD, mean absolute relative difference; CBG, capillary blood glucose |
| Funding Source (if any) | N/A |

2. Objectives

Diabetes is the number one cause of end stage kidney disease (ESKD) and need for dialysis. It is estimated that diabetes affects up to 40% of patients with ESKD³. Glycosylated hemoglobin (HbA1c) is the gold standard to assess glycemic control in patients with diabetes and indicates the average glycemia during the past 2-3 months. In subjects with ESKD; however, the accuracy of HbA1c is reduced because of anemia, shortened erythrocyte lifespan, erythropoietin therapy, among others factors. To overcome the limitations of HbA1c, continuous glucose monitoring (CGM) technology has been shown to provide a comprehensive glycemic control in patients with diabetes and may overcome the limitations of these methods in the ESKD population; however, the accuracy of CGM in ESKD has not been established.

About one fourth of patients with diabetes on dialysis therapy experience resolution of their hyperglycemia, as defined by an HbA1c less than 6.5%, without antidiabetic therapy. This

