Our study will use CGM to measure patients’ glucose with real-time levels as opposed to relying on surrogate markers like A1c. These results can give insight into the reality of glycemic control in these patients and can impact the best monitoring and treatment for patients with burnt-out diabetes. It is not known if patients with burnt-out diabetes have complete normoglycemia or if they may have episodes of (untreated) hyperglycemia, which may be associated with poor outcome. Accordingly, we will compare glycemic control by CGM in patients with burnt-out diabetes and non-diabetic patients with ESKD.

4. Study Endpoints

Primary safety and efficacy endpoints:

- 1) Frequency of overall and nocturnal hypoglycemia (< 70 mg/dl) by Dexcom G6 CGM (safety endpoint) ⁵².
- 2) Glycemic control, as measured by mean daily glucose concentration between groups by Dexcom G6 CGM (efficacy endpoint).

5. Study Intervention/Investigational Agent

The proposed CGM to be used in this study is the Dexcom G6, a factory-calibrated CGM system, that is innovative in many aspects: 1) it does not require finger stick glucose testing for calibration, 2) the sensor is small, compact, light-weight, 3) has no interference with several substances and drugs, and 4) effective glucose measures every 5 minutes (288 glucose measures per day).

6. Procedures Involved

Visit 1: All consenting subjects, with and without diabetes, will have a blinded Dexcom G6 CGM placed for up to 10 days (study duration). Consent procedure will be conducted during/after their hemodialysis sessions after explaining all study procedures. After providing informed consent, patients will have a sensor inserted by the study team. Insertion of the CGM sensor will be performed per manufacturer instructions and following an aseptic technique. After insertion of the sensors, providers will ensure proper hemostasis is achieved. Sensors will be removed if prolonged bleeding or severe pain occurs. Patients will be educated on study procedures and sensor care. The participants will be instructed to wear the CGM with the display off for 10 days while continuing regular, routine dialysis sessions. They will be instructed that the device will be removed at a future dialysis session after 10 days of wear.

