[name], Professor of Statistics at the School of Public Health will assist with data analysis. We will measure outcomes such as average daily glucose, time in range between 70-140 mg/dL, time in range between 70-180 mg/dL, fasting, premeal, 2 hours post meal, and nocturnal (10 PM-6:00 AM) glucose values, time (%) in hyperglycemia (>180 mg/dL, >250 mg/dL). In addition, we will collect information on glycemic variability by CGM.

Sample Size. This study will be a pilot study, as there is no preliminary data available for this patient population utilizing the Dexcom G6 CGM. Currently, there are 850 patients undergoing Hemodialysis at Emory Dialysis Centers. Up to 40% of these cases should be due to diabetes mellitus, and anywhere from \sim 25-35% of these patients should meet the definition of burnt-out diabetes, resulting in \sim 100 patients who should qualify as participants. Currently, we have identified \sim 20 patients with burnt-out diabetes on hemodialysis.

8. Data and/or Specimen Banking

Data collection records with personal identifiers will be stored in locked file cabinets. Presentation of the study results at regional or scientific meetings or in publications will not identify subjects. Access to research and confidential records will be limited to clinical investigators, research coordinators, and the IRB at Emory University.

9. Sharing of Results with Participants

Study results will be shared with the subjects at their request, including laboratory values, blood pressure measurements, and physical exam measurements.

10. Study Timelines

All consenting subjects, with and without diabetes, will have a Dexcom G6 CGM placed for up to 10 days (study duration). The CGM sensor will be removed after 10 days.

The anticipated time required to complete primary analysis of results is 6 -9 months

11. Inclusion and Exclusion Criteria

Inclusion Criteria

1. Be at least 18 years old
2. Dialysis treatment for more than 3 months
3. HbA1c less than 6.5% at the first clinic visit
4. Willing to wear a CGM for 10 days

Exclusion criteria

1. Have used insulin or any diabetes treatment during the last 3 months
2. Be pregnant or plan to become pregnant during the study
3. Known allergy to medical-grade adhesives

4. Taking acetaminophen (more than 1 gram every six hours) or hydroxyurea (may interfere with sensor membrane)
5. Current or anticipated use of stress steroid doses (prednisone \leq 5 mg or its equivalent is allowed)

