To assure each subject's confidentiality, data collected under this protocol will be coded and stored in a secure locked file cabinet with access limited to those directly related to the conduct of this study. Electronic versions of these data will be stored on a limited access, password protected, secure server with coded patient identifiers. Study participants will be assigned a code number that will be linked to their name. Only study personnel will have access to the linked name-code key. Except for the informed consent form, data will be marked solely with the participant's code number.

Statistical analysis

The primary endpoint in this study is to compare glycemic metrics including CGM and HbA1c in patients with burnt-out diabetes and in non-diabetic subjects with ESKD. We will first compare clinical characteristics including demographics, duration of diabetes and dialysis between patients with and without DR using two-sample t-tests or nonparametric Wilcoxon tests. We will perform multivariate linear regression to evaluate the group difference while accounting other possible confounders (patient age, type of dialysis) for the primary outcome. The secondary endpoints include compare daily mean glucose values between patients with burnt-out diabetes and non-diabetic subjects with ESKD, most recent HbA1c, comorbidities (hypertension, cardiovascular disease, heart failure, peripheral neuropathy, autonomic/GI neuropathy, cerebrovascular disease, peripheral vascular disease, depression, anxiety, cognitive impairment/dementia), adherence and barriers to screening recommendations, we will analyze continuous secondary outcomes in the same way that we propose for the primary endpoint. A p-value less than 0.05 will be considered significant. The data will be presented as means \pm SD. Statistical analysis will be performed using the SAS (version 9.2; SAS Institute, Cary, NC).

Confidentiality

All data and records generated during this study will be kept confidential in accordance with Institutional policies and HIPAA on subject privacy. The Principal investigator and other study personnel will not use data or PHI for any purpose other than conduction of the study. All PHI used will be de-identified and coded by the Principal investigator or designee. The code will be kept in a password protected computer file. PHI will be disclosed when required for audit by regulatory agency.

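### One unadjusted 0.05 rule covers three primary measures and ten further glycemic outcomes, with no testing order or exploratory label, so the chance of some false significant result exceeds 5%

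*Combined protocol and SAP*

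**What the plan says.** Section 7 (Statistical Analysis Plan) and Section 20 (Statistical analysis) both state: "A p-value less than 0.05 will be considered significant". Neither limits the rule to particular outcomes. No section gives a testing order, a multiplicity adjustment, or a statement that some results are exploratory.

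Section 4 puts two numbered items under its primary heading. The first, "Frequency of overall and nocturnal hypoglycemia (< 70 mg/dl) by Dexcom G6 CGM (safety endpoint"), holds two measures. The second is "Glycemic control, as measured by mean daily glucose concentration between groups by Dexcom G6 CGM (efficacy endpoint").

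Section 7 then widens the list: "We will measure outcomes such as average daily glucose, time in range between 70-140 mg/dL, time in range between 70-180 mg/dL". It continues with fasting, premeal, post-meal and nocturnal glucose, time above two thresholds, and glycemic variability.

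Section 20 describes the primary endpoint differently: "The primary endpoint in this study is to compare glycemic metrics including CGM and HbA1c in patients with burnt-out diabetes". It lists mean daily glucose and HbA1c as secondary, together with ten comorbidities and adherence and barriers to screening. Clinical characteristics are to be compared "using two-sample t-tests or nonparametric Wilcoxon tests". The primary outcome gets a linear regression adjusted for confounders, and continuous secondary outcomes are to be handled in the same way.

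The sample is "40 patients. 20 patients with burnt-out diabetes and 20 non-diabetic subjects with ESKD". No effect size, SD or power is given.

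**The concern.** A threshold of 0.05 limits the error of one test. Applied to each member of a list with no ranking, it does not limit the chance that some member crosses the line by luck. Here the list includes three measures headed primary and several overlapping summaries of the same sensor data, compared in 20 versus 20 patients. As written, the rule lets an isolated p-value below 0.05 on any of them be reported as a significant group difference, on the same footing as the main comparison. The protocol expects its results to inform monitoring and treatment (Section 3) and plans to present them at regional and national meetings (Section 26).

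**Working it through.** The plan states no overall error rate, so there is no figure of its own to reproduce. The only input it gives is 0.05 per test. Sidedness is not stated; two-sided tests are assumed.

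**Count of outcomes.**
- Section 4: overall hypoglycemia, nocturnal hypoglycemia, mean daily glucose = 3.
- Section 7, new items only: time in 70-140; time in 70-180; fasting, premeal, 2-hour post-meal and nocturnal glucose; time above 180; time above 250; glycemic variability = 9. Average daily glucose is already counted.
- Section 20: HbA1c = 1.
- Total glycemic outcomes: 3 + 9 + 1 = 13.

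**Independent tests.** With no true difference on any outcome, the chance of at least one p < 0.05 among k tests is 1 − 0.95^k.
- k = 3: 1 − 0.857 = 14.3%.
- k = 13: 1 − 0.513 = 48.7%.

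**Correlated tests.** Summaries of one sensor trace are correlated, but the documents give no correlations. Equal correlations of 0.5, 0.7 and 0.9 were therefore assumed in a simulation of two-sample t-tests, 20 versus 20, with 10,000 runs. The Monte Carlo standard error is at most √(0.25/10,000) = 0.5 percentage points. At zero correlation the simulation gave 14.1% and 48.5%, in agreement with the formula.

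| Outcomes tested | Independent (formula) | Correlation 0.5 | 0.7 | 0.9 |
|---|---|---|---|---|
| 3 (Section 4) | 14.3% | 12.6% | 11.0% | 8.3% |
| 13 (all glycemic) | 48.7% | 33.3% | 25.4% | 14.2% |

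**If the predicted differences are real.** The hypotheses under Specific Aims predict higher mean glucose and more time above 180 mg/dl in burnt-out diabetes. An outcome that truly differs cannot give a false positive. Removing only those two from the 13 leaves 11: 1 − 0.95^11 = 43.1% if independent. Removing mean glucose from the three leaves 2: 1 − 0.95² = 9.75%. Outcomes that overlap with the two would probably differ as well, which lowers the first figure further.

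**Upper case of 25.** Adding Section 20's ten comorbidities, adherence and barriers gives 13 + 12 = 25, and 1 − 0.95^25 = 72.3% if all are independent. If all 25 share one correlation of 0.5, 0.7 or 0.9, the figure is 47%, 32% or 17%. If only the 13 glycemic outcomes are correlated (0.5 to 0.9), and the comorbidities are independent and tested by Fisher's exact test (actual size 1.2-2.5% at assumed prevalences of 10-50%), it is about 31-53%.

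**After the change.** One named primary tested at 0.05 has an error of 5%. Holm across three measures compares the ordered p-values with 0.05/3 = 0.0167, 0.05/2 = 0.025 and 0.05, and holds the overall error at or below 5% whatever the correlation.

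**The case against.** The strongest defence is that this is a small observational pilot: "This study will be a pilot study, as there is no preliminary data available for this patient population utilizing the Dexcom G6 CGM". Readers of a pilot discount secondary p-values, and naming one primary would hold that test at 5%. This is fair as far as it goes. But the pilot label explains the absence of a sample-size calculation; it does not restrict the significance rule, and no section calls any outcome exploratory.

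A second defence is that the number of tests is inferred. Section 7 speaks of measuring outcomes and names no test for each. Only the efficacy item in Section 4 mentions a comparison between groups, and nocturnal episodes are a subset of overall ones. This stands as a condition: the figures hold if all the listed outcomes are tested. It also makes the correlated columns more realistic than the independent one.

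Three stronger readings are tempting, and the documents do not support them.
- A reader might infer that a false significant result is likely. At 13 outcomes the chance is below one half even under independence, and it falls to 14-33% at the assumed correlations.
- A reader might count 25 significance tests. Section 20 gives a method for continuous secondaries only and none for binary comorbidities. Section 6 describes collecting just four comorbidities (hypertension, coronary heart disease, heart failure, COPD), so most of the extra items have no described data collection. That is a separate defect.
- A reader might take the wording in Section 2 about proving a hypothesis to mean that any differing CGM metric would count as proof. The hypothesis in that passage is that CGM may be a better tool than HbA1c.

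**Conclusion.** The point holds in a limited form. The plan has one unadjusted 0.05 rule, three measures headed primary, ten further glycemic outcomes, and nothing that ranks them or marks any as exploratory. If all are tested and no difference is real, the chance of at least one false significant result is 8-14% for the three primary measures and 14-49% for the 13, over assumed correlations from 0.9 down to 0. It is lower where the predicted glucose differences exist.

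These ranges assume that each test holds its nominal 5% level and that correlations are equal across outcomes. The figure for 25 outcomes is an upper case only, and the conclusion does not depend on it. Naming one primary would settle the error for that comparison, but the sentence in Sections 7 and 20 would still label any other outcome significant. This is an inexpensive correction to what may be concluded; it does not undermine the design.

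**What to change.** First reconcile the status of mean daily CGM glucose. Section 1 makes it a secondary objective, Section 4 a primary efficacy endpoint, and Section 20 a secondary endpoint; Section 6 attaches the primary label to the safety outcome. The investigators should choose one primary comparison. The Section 4 efficacy endpoint is a natural candidate.

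Then replace the significance sentence in both Section 7 and Section 20, before the data are analysed. For example: *The between-group difference in mean daily CGM glucose is the single primary comparison, tested two-sided at 0.05. All other outcomes are exploratory. They are reported as group differences with 95% confidence intervals and without statements of significance.*

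If more than one Section 4 measure stays primary, state that Holm's procedure is applied across them, and accept some loss of power at 20 versus 20 because the smallest p-value must then fall below 0.0167 when there are three.

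The cost is wording, plus giving up the word significant for secondary metrics. No extra patients or data are needed.

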
29. Protocol Checklist

| Protocol Section | Added to the protocol? |
|--|---|
| External Collaborators- if applicable, add each external collaborator information and indicate whether that institution's IRB will review (or has already reviewed) that individual's engagement in human participants research activities) |  Yes |
| Funding Source* : Include the information for the funding entity for this study. Please explain if this study is covered by a sub-award or other pertinent information. Say "department" if you do not have any other funding. |  Yes |
| Objectives* : Describe the purpose, specific aims, or objectives and state the hypotheses to be tested |  Yes |
| Background* : Describe the relevant prior experience and gaps in current knowledge. Describe any relevant preliminary data. Provide the scientific or scholarly background for, the rationale for, and significance of the research based on the existing literature and how will it add to existing knowledge |  Yes |
| Study Endpoints* : Describe the primary and secondary study endpoints. Describe any primary or secondary safety endpoints. |  Yes |
| Study Intervention/Investigational Agent* : Describe the study intervention and/or investigational agent (e.g., drug, device) that is being evaluated. |  Yes |
| Drug/Device Handling : If the research involves drugs or devices, describe your plans to store, handle, and administer those drugs or devices so that they will be used only on participants and be used only by authorized investigators. If using a drug, explain if the control of the drug is managed by IDS (or VA/Grady/CHOA research pharmacies). If not, provide IDS exemption document. If a device, explain how the device is being stored and managed. |  Yes |
| If the drug is under an FDA REMS , plan to complete the REMS checklist found here, on the IRB website. |  Yes |
| If the drug is considered a controlled substance, make sure you have filled out this form. |  Yes |
| If applicable, identify the holder of the IND/IDE/Abbreviated IDE. An Emory investigator who holds an IND or IDE is considered to be a Sponsor-Investigator (S-I). If the study is under an S-I, review this section of our website for additional requirements. |  Yes |
| Procedures involved* : Describe and explain the study design and include a study schema. Describe all research procedures being performed and when they are performed, including procedures being performed to monitor participants for safety or minimize risks |  Yes |
| Procedures-Minimizing risk* : describe the procedures performed to lessen the probability or magnitude of risks. |  Yes |
| Procedures- Drug/Device Use : describe all drugs and devices used in the research and the purpose of their use and their regulatory approval status |  Yes |

Continuous Glucose Monitoring in Patients with End-Stage Kidney Disease and Burnt-Out Diabetes

| | |
|---|---|
| Procedures-Source Records* : describe source records that will be used to collect data about participants. Attach all surveys, scripts, and data collection forms to the submission. |  Yes |
| Procedures-Data collection* : describe what data will be collected during the study and how that data will be obtained |  Yes |
| Procedures- Long Term Follow Up* : once all research-related procedures are complete, what data will be collected during this period. If no data is collected after procedures are completed, please state in the submission. |  Yes |
| Data and Specimen Banking : describe where the specimens will be stored, how long they will be stored, how the specimens will be accessed, and who will have access to the specimens. Depending on the volume and nature of the collection, this may require a separate repository-specific IRB submission. The VA Data Repository SOP is required if the study is creating a data repository at the Atlanta VA. List the data to be stored or associated with each specimen. Describe the procedures to release data or specimens, including the process to request a release, approvals required for release, who can obtain data or specimens, and the data to be provided with specimens. |  Yes |
| Sharing of Results with Participants* : Describe whether results (study results or individual subject results, such as results of investigational diagnostic tests, genetic tests, or incidental findings) will be shared with participants or others (e.g., the participant's primary care physicians) and if so, describe how the results will be shared If applicable (e.g. for studies involving scans and/or panels of exploratory testing on specimens) Plan for managing the types of findings that might arise. This should include any secondary findings that are being sought actively, findings that might be anticipatable, and findings that might be un-anticipatable. Plan for recognizing, analyzing, and handling incidental findings and how incidental findings will be communicated to participants during the consent process. If the plan is not to disclose any findings, then this should be included. This plan might include the option for participants to opt-out of receiving incidental findings. Description of the research team's responsibilities following disclosure of a finding. This should detail educational information about the nature of the finding, how to seek care from a clinician or specialist, obtaining health insurance to secure treatment, and/or referral to a clinical specialist, if one is required. Reminder to include language in the consent form to let the participants know your plans for this – see Modular Language for Informed Consent Forms on IRB website) |  Yes |
| Study timelines* : describe the duration of an individual participant's participation in the study; anticipated time to enroll all study participants and the estimated date for the investigators to complete this study (complete primary analyses) |  Yes |
| Inclusion and Exclusion Criteria* : describe how individuals will be screened for eligibility and the criteria that define who will be included or excluded in your final study sample |  Yes |
| Population* : describe the study population and indicate specifically whether you will include or exclude each of the following special populations: 
 • Adults unable to consent • Individuals who are not yet adults (infants, children, teenagers) |  Yes |

Continuous Glucose Monitoring in Patients with End-Stage Kidney Disease and Burnt-Out Diabetes

- Pregnant women
- Prisoners

Note: you cannot exclude people with limited English proficiency unless you can demonstrate the scientific need for such exclusion.

Community Participation: For studies aimed at addressing issues that affect a certain community or group: How, if at all, will this study involve people from the target community in the design of the study? Conduct of the study? How will the results of the research be shared with the participants and/or the target community/ies?

If studying Race or Ethnicity, have you defined these terms, and explained their proposed mechanism of action if these characteristics will be used in an explanatory model?

Research with pregnant women, fetuses, or neonates: review [this checklist](#) to verify you have provided enough information to ensure the safety and well-being of this population. Yes

Research with neonates of uncertain viability: review [this checklist](#) to verify you have provided enough information to ensure the safety and well-being of this population. Yes

Research involving prisoners: review [this checklist](#) to verify you have provided enough information to ensure the safety and well-being of this population. Yes

Research involving children: review [this checklist](#) to verify you have provided enough information to ensure the safety and well-being of this population. Yes

Research involving cognitively impaired adults: review [this checklist](#) to verify you have provided enough information to ensure the safety and well-being of this population. Yes

Research involving economically or educationally disadvantaged persons: describe the additional safeguards that have been included in the study to protect the rights and welfare of these subjects Yes

Local Number of Participants*: Indicate the total number of participants to be accrued locally. If applicable, distinguish between the number of participants who are expected to be enrolled and screened, and the number of participants needed to complete the research procedures (i.e., numbers of participants excluding screen failures.) Yes

Provide your projected enrolling goals, including the percentage of participants according to sex and race.

Recruitment Methods*: Describe when, where, and how potential participants will be recruited. Describe the source of participants. Describe the methods that will be used to identify potential participants. Describe materials that will be used to recruit participants. Attach copies of these documents with the application. Yes

If including advertisements, attach the final copy of them. When advertisements are taped for broadcast, *attach the final audio/videotape*. You may submit the wording of the advertisement before taping to preclude re-taping because of inappropriate wording, provided the IRB reviews the final audio/videotape. Describe the amount and timing of any payments to participants. Reimbursement for expenses/travel?

If using contests or raffles as incentive, you must offer entry to all potential participants, not just those who enroll in the study/complete study-related procedures, per Georgia State Law.

Continuous Glucose Monitoring in Patients with End-Stage Kidney Disease and Burnt-Out Diabetes

| | |
|--|---|
| All research recruitment through social media needs to follow this guidance , which does not allow the use of personal social media accounts for some recruitment activities. | |
| Withdrawal of Participants* : Describe anticipated circumstances under which participants will be withdrawn from the research without their consent. Describe any procedures for orderly termination. Describe procedures that will be followed when participants withdraw from the research, including partial withdrawal from procedures with continued data collection. |  Yes |
| Risk to Participants* : List the reasonably foreseeable risks, discomforts, hazards, or inconveniences to the participants related to the participant's participation in the research. Include as may be useful for the IRB's consideration, a description of the probability, magnitude, duration, and reversibility of the risks. Consider physical, psychological, social, legal, and economic risks. If applicable, indicate which procedures may have risks to the participants that are currently unforeseeable. If applicable, indicate which procedures may have risks to an embryo or fetus should the subject be or become pregnant. If applicable, describe risks to others who are not participants. |  Yes |
| Potential Benefits to Participants* : Describe the potential benefits that individual participants may experience from taking part in the research. Include as may be useful for the IRB's consideration, the probability, magnitude, and duration of the potential benefits. Indicate if there is no direct benefit. Do not include benefits to society or others. |  Yes |
| Compensation to Participants* : Describe if/how subjects will be compensated for participation in this study. Indicate what method compensation will be delivered (e.g. cash, gift card, school credit). Describe the amount and timing of any payments to participants. How much? What kind? Is tax information required? (if so, must be reflected in the informed consent form). Will payments be pro-rated if a participant withdraws early? |  Yes |
| Data Management and Confidentiality* : Describe the data analysis plan, including any statistical procedures or power analysis. Describe the steps that will be taken to secure the data (e.g., training, authorization of access, password protection, encryption, physical controls, certificates of confidentiality, and separation of identifiers and data) during storage, use, and transmission. Describe any procedures that will be used for the quality control of collected data. |  Yes |
| Describe how data or specimens will be handled study-wide* : What information will be included in that data or associated with the specimens? 
 • Where and how data or specimens will be stored? • How long the data or specimens will be stored? • Who will have access to the data or specimens? • Who is responsible for receipt or transmission of the data or specimens? • How data or specimens will be transported? |  Yes |
| Data Monitoring and Participants Safety (if this study is more than minimal risk, this section is required): |  Yes |

Continuous Glucose Monitoring in Patients with End-Stage Kidney Disease and Burnt-Out Diabetes

Ensure that you review our [Data and Safety Monitoring plan guidance](#) for specific details about this section, and examples of what the IRB will be requiring according to the level of risk.

If a DSMB is needed, please describe the composition of the board (if not already detailed in the protocol). [Review this guidance](#) for more information. If the sponsor protocol does not contain all required information, please in this section.

Describe the plan to periodically monitor the data at the site level according to risk level.

Include the appropriate completed monitoring table, if applicable.

Description of the plan for notifying the IRB of reportable events, whether the sponsor requires reporting above and beyond the Emory IRB reporting requirements, and if so, a description of the requirements and plan for meeting them.

Please address the specific details below. If deemed not applicable, please provide rationale:

Subject safety:

- Specific subject safety parameters
- Frequency of subject safety observations
- Individual responsible for safety monitoring
- Subject stopping rules – under what conditions will a subject be removed from study participation and who will make the decision?
- Study stopping rules - under what conditions will the study be modified or stopped and who will make the decision?
- Reporting mechanisms (i.e. Deviations, adverse events, UPs)

Data Integrity:

- Specific data elements to be reviewed
- Frequency of monitoring data, points in time, or after a specific number of participants
- Individual responsible for data monitoring

Additional considerations for FDA regulated trials

Depending on the procedures affecting risks to participants, the site monitoring plan should specify:

- Categorization of activities done centrally and those on-site if applicable
- Monitoring methods (may include centralized/remote, on-site, and self-monitoring)
- Reference to any tools used (i.e. checklists)
- Identification of events that may trigger changes
- Identification of deviations or failures that would be critical to study integrity

Provisions to Protect the Privacy Interests of Participants*:

- Describe the steps that will be taken to protect participants' privacy interests. "Privacy interest" refers to a person's desire to place limits on whom they interact with or whom they provide personal information.
- Describe what steps you will take to make the participants feel at ease with the research situation in terms of the questions being asked and the procedures being performed. "At ease" does not refer to physical discomfort, but the sense of

Yes

Continuous Glucose Monitoring in Patients with End-Stage Kidney Disease and Burnt-Out Diabetes

| | |
|--|---|
| 
intrusiveness a participant might experience in response to questions, examinations, and procedures.
 
 Indicate how the research team is permitted to access any sources of information about the participants. | |
| 
Economic Burden to Participants*: Describe any costs that participants may be responsible for because of participation in the research.
 |  Yes |
| 
Consent Process*: Describe where the consent process will take place, any waiting period available between informing the prospective subject and obtaining the consent; and the process to ensure ongoing consent.
 
Describe the role of the individuals listed in the application as being involved in the consent process; the time that will be devoted to the consent discussion; steps that will be taken to minimize the possibility of coercion or undue influence; and steps that will be taken to ensure the participants' understanding.
 
Note: If you are planning to obtain consent via electronic signature, please review this document. Additional guidance on consent documentation and process can be found on our website, under the consent toolkit.
 |  Yes |
| 
Consent Process-Non-English-Speaking Participants*:
 
Indicate what language(s) other than English are understood by prospective participants or representatives.
 
If participants who do not speak English will be enrolled, describe the process to ensure that the oral and written information provided to those participants will be in that language.
 
Indicate the language that will be used by those obtaining consent.
 
If you checked N/A, please provide reasoning of why subjects with limited English proficiency are excluded.
 
Note: if you stated that subjects with LEP will be enrolled, you are approved for the use of the Emory IRB short forms. Please read the guidance about the use of short forms here.
 |  Yes |
| 
Consent Process-Children: After determining if the subject is a child per GA law (or if enrolled outside GA, per state/country law), please describe whether parental permission will be obtained from:
 
 Both parents unless one parent is deceased, unknown, incompetent, or not reasonably available, or when only one parent has legal responsibility for the care and custody of the child. One parent even if the other parent is alive, known, competent, reasonably available, and shares legal responsibility for the care and custody of the child. 
Describe whether permission will be obtained from individuals other than parents, and if so, who will be allowed to provide permission. Describe the process used to determine these individuals' authority to consent to each child's general medical care.
 
When assent of children is obtained describe whether and how it will be documented per Emory Policies and Procedures
 |  Yes |
| 
Consent Process-Cognitively Impaired Adults: describe the process to determine whether an individual is capable of consent. The IRB allows the person obtaining assent to document assent on the consent document and does not routinely require assent documents and does not routinely require children to sign assent documents.
 |  Yes |

| | |
|--|---|
| 
Consent Process-Adults Unable to Consent: List the individuals from whom permission will be obtained in the order of priority. (E.g., durable power of attorney for health care, a court-appointed guardian for health care decisions, spouse, and adult child.) For research conducted in the state, review "46 LEGALLY AUTHORIZED REPRESENTATIVES AND SURROGATE CONSENT" to be aware of which individuals in the state meet the definition of "legally authorized representative." For research conducted outside of the state, provide information that describes which individuals are authorized under applicable law to consent on behalf of a prospective subject to their participation in the procedure(s) involved in this research. Describe the process for the assent of the participants. Indicate whether:
 
• Assent will be required of all, some, or none of the participants. If some, indicated, which participants will be required to assent and which will not.• If assent will not be obtained from some or all participants, an explanation of why not. 
Describe whether the assent of the participants will be documented and the process to document assent. The IRB allows the person obtaining assent to document assent on the consent document and does not routinely require assent documents and does not routinely require participants to sign assent documents
 |  Yes |
| 
Waiver or Alteration of Consent Process (consent will not be obtained, required information will not be disclosed, or the research involves deception) Review the Emory IRB waiver document to ensure you have provided sufficient information for the IRB to make these determinations. If the research involves a waiver of the consent process for planned emergency research, please review the "CHECKLIST: Waiver of Consent for Emergency Research (HRP-419)" to ensure you have provided sufficient information for the IRB to make these determinations.
 |  Yes |
